4.3.2 Exclusion Criteria

For the purposes of this retrospective data collection, it is desirable that eligibility criteria are the least restrictive possible. Therefore, there are no exclusion criteria for patients in this study.

5 PLANNED ANALYSES

5.1 Interim Analysis

No interim analysis is planned for this study.

5.2 Final Analysis

All planned analyses identified in this SAP will be performed by IQVIA Real World Solutions (RWS) Biostatistics following the final database lock.

6 ANALYSIS SETS

6.1 Enrolled Set [ENR]

The enrolled set (ENR) will contain all enrolled patients.

6.2 Full Analysis Set [FAS]

The full analysis set (FAS) will contain all enrolled patients who fulfilled eligibility criteria.

6.3 HR+ Analysis Set [HRAS]

The HR+ analysis set (HRAS) will contain all HR+ patients from the full analysis set, i.e., who had either Estrogen receptor (ER) positive or Progesterone receptor (PR) positive or both positive at primary breast cancer diagnosis.

Document: ZZA65950_NEAR_SAP_v2.0

Author: [name]

Version Number: 2.0

Version Date: 22SEP2023

7 GENERAL CONSIDERATIONS

7.1 Patient Identification Period

The patient identification period is the eligibility time window for selection of patients who initiated neratinib treatment within the EAP in Europe between 01 August 2017 and 31 December 2020.

7.2 Index Date

The index date is defined as the date of first neratinib initiation through the EAP.

7.3 Baseline Period

Data analyzed for the baseline period will consist of all relevant data available prior to the first dose of neratinib initiation (index date).

7.4 Neratinib Initiation

Data analyzed for the neratinib initiation period will consist of all relevant data collected within +/- 30 days of index date.

7.5 Study Entry Date

The study entry date is defined as the cut-off date until when the eligible patients' data as obtained from medical charts are abstracted for analysis in the study. This date will be the same for all patients and corresponds to the date of first patient in, 05 July 2022.

7.6 Study Observation Period

The overall study observation period extends from baseline period to study entry date.

7.7 Follow-up Period

The follow-up period for each patient extends from index date to end of the study observation period. Patients' data collection will be censored at date of death, or among patients who did not die, at the

end of the study observation period or at the date of last visit, whichever occurs first. Patients will have variable follow-up periods length, depending on their index date and last contact date.

7.8 End of Observation (EOB) Date

The end of observation (EOB) date is defined as the study entry date, date of death or date of last contact, whichever happens first.

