4 RESEARCH METHODS

4.1 STUDY DESIGN

This is a European, multi-country, multicenter, retrospective, observational, longitudinal study to describe the demographic characteristics and clinical profiles of patients with HER2+ breast cancer who were treated with neratinib as an extended adjuvant therapy, in the context of the EAP in Europe. Eligible patients will be selected among those having received at least one dose of neratinib in this EAP, between August 01, 2017 and December 31, 2020 (the patient identification period). The decision to prescribe neratinib was taken prior to and independent of the proposal to select a patient into this study and all data will be retrospectively collected from the patients' medical charts.

The definitions of terms used to describe various phases of this study are as below:

Patient Identification Period: Time period eligibility for selection of patients who initiated neratinib treatment within the EAP in Europe, from August 01, 2017 until December 31, 2020.

 Pierre Fabre TEMP CQA 0092 V2.0 Owning site : CORPORATE QA	Template to use for writing Corporate document, except Corporate policy and form, WORD in english	Page 12/29
--	--	------------

Study Entry Date: The cut-off date until when the eligible patients' data as obtained from medical charts are abstracted for analysis in the study.

Index Date: The index date is defined as the date of neratinib initiation

Baseline Period: All relevant data available prior to the first dose of neratinib initiation (index date)

Follow-up period: The period starting from neratinib initiation within the EAP in Europe (index date) until data cut-off date (end of the study observation period). Patients will be censored at date of death, or among patients who did not die, the data cut-off date (end of the study observation period) or date of last visit, whichever occurs first. Patients will have variable follow-up time periods, depending on their index dates and last contact dates.

A study completion follow-up will be performed for all enrolled patients for whichever of the following cases that come first:

- a. At the end of the study observation period
- b. Upon study withdrawal
- c. After attempts to trace patients lost to follow-up
- d. Deceased patients

Study Observation Period: The overall study observation period includes the period from baseline till study entry date, and all available data for each patient will be collected until the end of the observation period

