4.3.3 Exploratory outcomes

Effectiveness will be evaluated only on HR+ patients based on the following outcomes, until the end of study observation period:

1. Characterization of first recurrence patterns (location, distribution, size, date)
2. iDFS, defined as the time from neratinib treatment initiation to:
 - a. First ipsilateral invasive breast cancer recurrence
 - b. First regional invasive breast cancer recurrence
 - c. First contralateral invasive breast cancer recurrence
 - d. First distant tumor recurrence
 - e. Death attributable to any cause.
3. DDFS, defined as the time from neratinib treatment initiation to the first distant tumor recurrence or death from any cause.
4. Incidence of CNS metastasis (either isolated or concurrent with other metastatic sites), defined as the time from neratinib initiation to CNS recurrence as first distant recurrence.
5. OS, defined as the time between neratinib treatment initiation (for early breast cancer) and death (due to any cause)

The following key data items will be collected for the **first three** clinical exploratory outcomes:

1. Recurrences after neratinib initiation: date of documented recurrence and site of recurrence, including size and distribution.
 - a. Invasive ipsilateral breast tumor recurrence
 - b. Invasive contralateral breast cancer
 - c. Local/regional invasive recurrence
 - d. Appearance / Occurrence of metastasis /Distant recurrence, including CNS metastasis
2. Date of death and cause of death (related to this cancer, non-breast cancer related, related to another cancer, related to neratinib, other, unknown)
3. Date of last patient visit during follow-up (if applicable)

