4.4 DATA SOURCES

Data for each patient will be collected from the date of neratinib treatment initiation up to the end of the study observation period (or date of death, study withdrawal, or lost-to-follow-up, if these come

 Pierre Fabre TEMP CQA 0092 V 2.0 Owning site : CORPORATE QA	Template to use for writing Corporate document, except Corporate policy and form, WORD in english	Page 20/ 29
---	--	-------------

first). Patients lost to follow-up will be censored at the date of their last available medical record. A data collection schedule is provided in Table 1. Data at following timepoints during the Study Observation Period will be collected: (a) at baseline; (b) at the index date; (c) 1 month, 2 months, 3 months, 6 months, 12 months after the index date; and (d) at any additional tumor assessment visits

The source of collected data will include all elements that constitute a reliable source of patient-level information and are available at the center. This includes inpatient medical charts (e.g., consultation notes, discharge summaries, laboratory test results, recorded prescription data and any other documentation of communication with other health care providers). The center investigator will be responsible for ensuring that all the required data is collected and entered into an eCRF. The data will be anonymized during the entry into the eCRF by using an algorithm which generates a patient number without any indication of the patient. This anonymization will be maintained in the database used for statistical analysis.

Key data items that will be collected are listed in section 4.3, Study outcomes.

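### iDFS, DDFS and CNS metastasis are censored with a survival rule (last known alive or last contact), which can credit recurrence-free time that nobody observed

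*SAP*

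**What the plan says.** The documents give several end-of-follow-up rules.

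- **SAP 7.8** (EOB): "The end of observation (EOB) date is defined as the study entry date, date of death or date of last contact, whichever happens first". Tables 4, 5 and 6 use EOB for patients with no event, lost to follow-up or withdrawn, for iDFS, DDFS and CNS metastasis. Table 7 uses it for OS.
- **SAP 13.2**, covering all time-to-event outcomes: event-free and lost patients are censored when last known alive. That is the study entry date for those alive at end of study and the last contact for those lost.
- **SAP 7.7**: patients who did not die are censored at the "end of the study observation period or at the date of last visit, whichever occurs first". The next sentence says: "Patients will have variable follow-up periods length, depending on their index date and last contact date".
- **Protocol 4.1**: "the data cut-off date (end of the study observation period) or date of last visit, whichever occurs first", followed by "Patients will have variable follow-up time periods, depending on their index dates and last contact dates".
- **Protocol 4.4**: "Patients lost to follow-up will be censored at the date of their last available medical record".

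Neither document defines visit or contact, or says whether a contact includes a check for recurrence. Protocol 4.3.3 lists the date of the last patient visit as a key data item for the first three exploratory outcomes. The date conventions in SAP Appendix 1 list the last contact date and no last-visit date. SAP 7.10, which lists changes from the protocol, does not mention the censoring date.

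**The concern.** Knowing that a patient is alive on a date is the right basis for censoring OS. It is not enough for a recurrence endpoint, where event-free time is observed only as far as someone has recorded recurrence status. Under SAP 13.2, a patient known to be alive at end of study counts as recurrence-free to 05 July 2022, however old the last disease information is.

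Any time credited beyond that information stays in the risk set but cannot produce an event. The apparent recurrence hazard falls, iDFS and DDFS move up, and CNS incidence moves down. The reverse Kaplan-Meier follow-up in SAP 8.2 is overstated for these endpoints even if no recurrence is missed, because the censoring date itself is too late.

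The rules can also give one patient different dates, so the programmer has to choose among them.

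**Working it through.** **1. The rules side by side (hypothetical patient).** She was last examined on 05 January 2022, had an administrative contact on 05 April 2022, and is recorded as alive at end of study with no recurrence.

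- Last visit (SAP 7.7, Protocol 4.1): 05 January 2022.
- Last contact (SAP 7.8): 05 April 2022, which is 90 days or 90/30.4 = 3.0 months later.
- Alive at end of study (SAP 13.2): 05 July 2022, which is 181 days or 181/30.4 = 6.0 months after the examination.

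Only the first date is tied to an examination. The formulas in SAP 13.2.1 to 13.2.3 do not settle the matter: they count to a last available date that is not defined, while the OS formula counts to the date last known alive.

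**2. Inputs for the size.** The plan states no figure for this point, so there is none to reproduce.

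- Index dates: 01 August 2017 to 31 December 2020 (SAP 7.1), assumed uniform.
- Cut-off: 05 July 2022 (SAP 7.5).
- Hazard: the 2-year iDFS of 93.9% in the neratinib arm of the pivotal trial (Protocol section 2), assumed exponential. h = -ln(0.939)/24 = 0.00262 per month. True iDFS is then exp(-18h) = 95.4% at 18 months and exp(-36h) = 91.0% at 36 months.
- Gap g between the last recurrence information and the cut-off: not given. Assumed 3, 6 or 12 months for every patient, with all events in the gap missed.

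**3. Potential follow-up** by the SAP formula (days + 1)/30.4:

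- Shortest: (551 + 1)/30.4 = 18.2 months.
- Longest: (1799 + 1)/30.4 = 59.2 months.

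Every patient's cut-off lies beyond 18 months, the last landmark in SAP 8.2.

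**4. Kaplan-Meier under the gap.** Let U be potential follow-up, uniform on 18.16 to 59.21. At time t the risk set has two parts:

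- A(t), patients whose events would still be seen (U > t + g): (59.21 - max(18.16, t + g)) × exp(-ht).
- B(t), patients counted at risk whose events would not be seen (t < U < t + g): the integral of exp(-h(u - g)) over that range.

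The apparent hazard is h × A/(A + B), and apparent iDFS is exp(-integral of that hazard). Nothing is lost before t = 18.16 - g. At t = 36 the observable share A/(A + B) is about (23.21 - g)/23.21, or 87%, 74% and 48%.

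| Gap | 18 months (true 95.4%) | Shift | 36 months (true 91.0%) | Shift |
|---|---|---|---|---|
| 3 months | 95.4% | +0.02 | 91.4% | +0.4 |
| 6 months | 95.5% | +0.1 | 91.9% | +0.9 |
| 12 months | 95.8% | +0.4 | 93.1% | +2.1 |

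**5. Milder scenarios (simulation, same hazard and dates).**

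- 10% to 30% of patients lost, with last contact 1 to 12 months after last visit: 18-month shift 0.01 to 0.32 points, 36-month shift up to 0.7.
- No loss, last visits spread uniformly over up to 12 months before cut-off: at most 0.15 points at 18 months and 1.0 at 36 months.

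**6. Reverse Kaplan-Meier.** An event-free patient's recurrence follow-up is overstated by the whole gap: 3, 6 or 12 months in the scenarios of step 4.

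**The case against.** The best defence is that visit and contact may be meant as one date. SAP 7.7 and Protocol 4.1 use both terms in adjacent sentences, and neither document defines them. That stands against reading the text as a deliberate move from visit to contact. It does not rescue SAP 13.2, whose rule for patients alive at end of study depends on neither term.

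Second, charts are abstracted after the cut-off, and the sources include "any other documentation of communication with other health care providers". A patient documented as recurrence-free after 05 July 2022 is rightly censored on that date, and a recurrence found elsewhere can reach the chart. This stands too. It makes the over-credited time conditional and means that the last clinic visit is not itself the right anchor.

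Third, censoring event-free patients at an old visit while counting recurrences up to cut-off could bias iDFS downward. The fix must meet this, and it does so by keeping the cut-off date for patients whose status is documented on or after it.

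Three stronger readings are tempting but not supported:

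- **That the gap is built into the design, because consent is sought around or after the cut-off and so counts as a contact.** No section says that a consent approach is the last contact. SAP 13.2 takes that date from the eCRF, and in France a posted letter without reply is enough (Protocol 4.2.2.2).
- **That the bias differs by consent route.** The eligibility note describes the waiver for deceased or lost patients. Any difference may simply follow loss status.
- **That the hazard is understated by the gap's share of mean follow-up.** With mean follow-up (18.2 + 59.2)/2 = 38.7 months, this would put 36-month iDFS at 91.7%, 92.3% or 93.7%. Time after month 36 cannot enter a 36-month Kaplan-Meier estimate, so the table above applies.

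**Conclusion.** The point holds. The plan censors three recurrence endpoints with a rule suited to survival, its own sections disagree on the date, and the difference from the protocol's last-visit wording is not declared. The direction is towards better iDFS and DDFS, lower CNS incidence and longer apparent follow-up.

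The effect on the planned landmark estimates is small: up to about 0.4 points at 18 months. For scale, with 120 patients the 95% half-width there is about 1.96 × sqrt(0.954 × 0.046/120) = 3.7 points. The later part of the curve, which SAP 8.2 also presents, is affected more: about 0.4, 0.9 or 2.1 points at 36 months. Reverse Kaplan-Meier follow-up is affected by the full gap.

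These sizes rest on an assumed common gap, all gap events missed, a constant hazard from another trial and uniform index dates. Missing every event in the gap is the extreme case. Applying the shift to all iDFS events also overstates it, since deaths come from a separate eCRF page. The endpoints are exploratory and descriptive. The case for change is that the rule does not fit these endpoints and is cheap to correct.

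**What to change.** - **OS:** keep EOB / last known alive.
- **iDFS, DDFS and CNS metastasis:** censor event-free patients at the earlier of the study entry date and the last date with documented recurrence status in any chart source. A patient documented recurrence-free on or after 05 July 2022 is censored at 05 July 2022.
- **Deaths:** leave the death rows of Tables 4 to 6 unchanged.
- **Alignment:** define visit and contact, and apply the rule in SAP 7.7, 7.8, 13.2 and Tables 4 to 6 together. Changing the tables alone would leave 13.2 in contradiction. List the change in SAP 7.10.
- **Sensitivity analysis:** repeat the three endpoints with EOB censoring, so that the reader can see how much the choice matters.

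The cost is SAP wording, one derived date and one repeat of the analysis. The protocol already plans to collect the last-visit date. If the eCRF holds no separate date for recurrence status, the visit date is the nearest substitute and should be described as such. The downside is shorter recurrence follow-up for patients without recent disease information, which could be substantial if such gaps are long.

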7.9 Software Version

All analyses will be conducted using statistical analysis system (SAS)[®] version 9.4 or higher (SAS Institute, Cary, NC, USA).

7.10 Changes from Protocol

In the eCRF an additional inclusion criterium was considered, i.e., the patient was diagnosed with HER2+ breast cancer. For analysis proposes this additional criterium is considered in the analysis datasets and used in the identification of the FAS.

In the protocol the study entry date was defined as the cut-off date until when the eligible patients' data as obtained from medical charts are abstracted for analysis in the study. Based on a request from Pierre Fabre, the study entry date was assigned in the SAP to the date of first patient in, 05 July 2022, to ensure that all patients have the same cut-off date.

In section 8.2, two additional periods were considered in the time to event analysis, i.e., in protocol the intervals considered were 1, 3, 6, 9 and 12 and for analysis the periods that will be considered are 1, 3, 6, 9, 12, 15 and 18.

The subgroup analysis considered in section 8.4 has been updated from protocol. The nodal status at initial diagnosis and the tumor size at initial diagnosis were removed from the subgroups of interest. The subgroup previous adjuvant or neoadjuvant therapy was defined in the protocol as "Yes/ No" and will be updated to "Neoadjuvant + Post neoadjuvant treatment/ Adjuvant only".

The following subgroups analysis was added: according to EU label status, Concomitant Corrective Antidiarrheal, Concomitant Prophylaxis Antidiarrheal, Initial Dose of Neratinib.

In the protocol the exploratory analysis was planned to be performed only in HR+ patients, it will be analyzed separately for HR+ / HR- patients.

8 STATISTICAL CONSIDERATIONS

8.1 Descriptive Statistics

All data collected for the study will be summarized with appropriate statistics. For continuous variables, the number, mean, standard deviation, median, 1st and 3rd quartiles, minimum and maximum will be provided, as well as the associated 95% CI, when appropriate. For categorical variables, the numbers and percentages will be provided, as well as the associated 95% CI, when appropriate. Percentages will be computed among patients with available data.

8.2 Time to Event Analysis

The cumulative incidence of events of interest will be assessed using the Kaplan Meier method and will be presented graphically (Kaplan Meier curve). For Kaplan-Meier, the number of events, number of censored data points, median survival time, Q1 and Q3 survival time and corresponding two-sided 95% CI will be presented. Estimates of the proportion of patients not presenting the event of interest at 3-month intervals (1, 3, 6, 9, 12, 15, 18 months) and the corresponding two-sided 95% CIs will be provided. Censoring rules relative to each event of interest are further detailed in the corresponding analysis sections (see section 13.2).

To determine the potential follow-up time the reverse Kaplan-Meier method will be applied, in this method the events and censors are reversed thus the event of interest (see section 13.2) becomes the censor. For the reverse Kaplan Meier, the number of events, number of censored data points, median follow-up time, Q1 and Q3 follow-up time and corresponding two-sided 95% CI will be presented.

If number of patients is large enough, Cox regression analysis may be performed to adjust for predefined baseline covariates. In this case and for time to Central Nervous System Metastasis, the Fine and Gray model will be used to account for the competing risk of disease recurrences.

Where applicable, the Log rank test will be used to compare time-to-event and survival data between subgroups in an exploratory manner.

8.3 Missing Data

Due to the nature of the study, there will likely be missing data; data may be missing or not recorded in the patient's chart. Generally, missing data will not be imputed, and data will be analyzed and presented as they are recorded in the database. Missingness for all variables will be indicated in descriptive tables. Partial date handling is described in Appendix 1. Listings will present the dates as reported in their original, non-imputed format (i.e., 'UNK' for the missing day, month and/or year).

8.4 Examination of Subgroups

The following subgroups are of interest, based on patient characteristics at neratinib initiation (index date) or primary diagnosis of breast cancer. Analyses of primary, secondary, and exploratory outcomes may be performed for some or all these subgroups, subject to pertinence and the number of patients in each subgroup:

- EU label status: Yes, No
 - Yes, defined as, HR+ patients with initiation of Neratinib ≤ 1 year from trastuzumab-based treatment completion in adjuvant setting (EU Label population)
 - No, otherwise
- Pathologic stage (AJCC classification) at primary breast cancer: Stage I, Stage II+III
 - If missing, derived as in 2
- Residual disease after neoadjuvant treatment (pathologic complete response [pCR]): pCR, No pCR

- Risk: Low risk (Stage I or N- or pCR), High risk (Stage II/III or N+ or no pCR)
 - N-, defined as, the electronic case report form (eCRF) nodal status category of NX or N0
 - N+, defined as $N \geq 1$ nodal
- Previous adjuvant or neoadjuvant therapy ⁽²⁾: Neoadjuvant + Post neoadjuvant treatment, Adjuvant only
 - Neoadjuvant + Post neoadjuvant, defined as, at least one neoadjuvant and one adjuvant treatment
 - Adjuvant only, defined as, at least one adjuvant treatment and no neoadjuvant
- Prior trastuzumab-based regimen overall (neoadjuvant or adjuvant): Trastuzumab only, Trastuzumab and Pertuzumab, Trastuzumab emtansine (T-DM1), Other anti HER2
- Prior trastuzumab based regimen the last treatment in adjuvant setting before Neratinib initiation: Trastuzumab only, Trastuzumab and Pertuzumab, Trastuzumab emtansine (T-DM1), Other anti HER2
- Hormone Receptor at Primary Breast Cancer Diagnosis: HR+, HR-
 - HR+, defined as either ER or PR or both are positive
 - HR-, defined as if ER and PR are negative
- Concomitant Corrective Antidiarrheal: Yes, No
- Concomitant Prophylaxis Antidiarrheal: Yes, No
- Initial Dose of Neratinib: <240mg, 240mg, >240mg

Table 2 AJCC staging

Primary tumor (T)	Regional lymph nodes (N)	Distant metastasis (M)	Stage
Tis	N0	M0	0
T1	N0	M0	IA
T0	N1	M0	IB
T1	N1	M0	IB
T0	N1	M0	IIA
T1	N1	M0	IIA
T2	N0	M0	IIA
T2	N1	M0	IIB
T3	N0	M0	IIB
T0	N2	M0	IIIA
T1	N2	M0	IIIA
T2	N2	M0	IIIA
T3	N1	M0	IIIA
T3	N2	M0	IIIA
T4	N0	M0	IIIB
T4	N1	M0	IIIB
T4	N2	M0	IIIB
Any T	N3	M0	IIIC
Any T	Any N	M1	IV

N2 and N3 are not collected in the CRF, this regional lymph node categories will be identified by “ ≥ 4 ” lymph nodes involved.

